4.9.2 Immunogenicity data

Immunogenicity data will be analyzed descriptively by treatment group. No statistical tests are planned. Baseline ADA-positive subjects will be calculated as a percentage of the total number of subjects whose baseline samples were tested for ADA. Titer will be reported as median and interquartile range.

4.9.3 Clinical laboratory assessments

Clinical laboratory test results will be flagged as to whether the result is below, within, or above the respective reference range. The number of values outside of the reference range will be counted.

Results from the following laboratory parameters, recorded at the Screening, Dosing, and Follow-up visits will be summarised by treatment and time point:

CONFIDENTIAL

Sponsor:	Zealand Pharma A/S	Protocol Number:	ZP4207-16137
----------	--------------------	------------------	--------------

- **Clinical biochemistry:** sodium, potassium, calcium, glucose, urea, creatinine, total bilirubin, AST, ALT, gamma-glutamyltransferase, alkaline phosphatase, total protein, C-reactive protein. HbA1c and C-peptide at screening visit only.
- **Hematology:** hemoglobin, red blood cell count (erythrocytes), hematocrit, platelet count (thrombocytes), total white blood cell count (leukocytes).
- **Coagulation:** international normalized ratio, fibrinogen (at screening visit only).
- **Urinalysis:** pH, blood (leukocytes and erythrocytes), protein, glucose, ketones, nitrite.

Categorical and numeric variables will be presented separately.

Shift tables for the hematology and biochemistry laboratory parameters comparing values below, within, and above the normal reference range will be presented using standard reference ranges.

Abnormal laboratory findings (e.g. biochemistry, hematology, and urinalysis) that are judged by the investigator as clinically significant will be recorded as AEs or SAEs if they meet the definition of an AE or SAE. Clinically significant abnormal laboratory findings or other abnormal assessments that are detected during the trial or are present at baseline and significantly worsen following the start of the trial will be reported as AEs or SAEs.

4.9.4 Other safety data

Incidence of rescue infusion of IV glucose during the hypoglycemic clamp procedure will be analyzed using descriptive statistics (frequency and percentage) by treatment group. Inferential treatment group comparisons will be assessed via pairwise tests of independent binomial proportions (dasiglucagon versus placebo, GlucaGen versus placebo).

Time to first rescue infusion of IV glucose during the hypoglycemic clamp procedure will be evaluated using a KM time to event statistical model, with treatment group and injection site (abdomen, buttock, or thigh) as stratification factors. Differences between the KM curves (dasiglucagon versus placebo, GlucaGen versus placebo) will be evaluated inferentially using pairwise two-sided stratified log-rank tests. If the endpoint is never met, the time of the last plasma glucose measurement will be the censoring time.

Vital signs, physical examination, 12-lead ECG and local tolerability data will be summarized using descriptive statistics.

4.9.5 Vital signs

The following vital signs will be summarized for the Safety analysis set subjects:

- Systolic and diastolic blood pressure (mmHg)
- Pulse rate (beats/min)
- Body temperature (°C)

At the dosing visit, measurements will be taken prior to the start of the insulin-induced hypoglycemic procedure (within 30 minutes) and at 30, 90, and 300 minutes after dosing. The

CONFIDENTIAL

Sponsor:	Zealand Pharma A/S	Protocol Number:	ZP4207-16137
----------	--------------------	------------------	--------------

actual time of the assessment should not deviate from the nominal time by more than ± 10 minutes. In addition to the pre-specified assessments, blood pressure and pulse may be assessed at any time during the trial at the discretion of the investigator.

Vital signs data and changes from baseline in vital signs will be summarized by treatment group and time point where appropriate using standard descriptive statistics.

4.9.6 Physical examination

A complete physical examination will be performed at Screening and Follow-up visits; after study drug has been administered any clinically significant changes in physical examination findings will be recorded as AEs. Physical examination data will be summarized using descriptive statistics and will be provided in the listings.

4.9.7 12-Lead ECG

At the dosing visit, measurements will be taken prior to the start of the insulin-induced hypoglycemic procedure (within 30 minutes), and at 20, 35, 45, 60 and 300 minutes after dosing. The actual time of the assessment should not deviate from the nominal time by more than ± 5 minutes.

The quantitative ECG assessments (heart rate, PQ, QRS, QT, QTcB) will be summarised using descriptive statistics for actual values and changes from baseline to each time point by treatment and time.

4.9.8 Local tolerability

At the dosing visit, immediately prior to treatment administration, it should be verified that the injection site is normal. To ensure all injection site assessments are performed at the injection site, the site will be marked with a pen prior to injection. Local tolerability at the injection site will be assessed at 30, 120, and 300 minutes after dosing. The actual time of the assessment should not deviate from the nominal time by more than ± 10 minutes.

The local tolerability at the injection site will be evaluated by means of the following assessments: spontaneous pain, pain on palpation, itching, redness, edema, induration/infiltration, and other. Each of these assessments will be reported on a scale of 0 (none), 1 (mild), 2 (moderate), and 3 (severe). The evaluation and the actual time of the assessment will be recorded. Local tolerability data will be summarized using descriptive statistics by injection site and overall, and will be provided in the listings.

4.10 Adjustment for Covariates

The primary endpoint will be additionally analyzed using a Cox Proportional Hazards (CPH) time to event statistical model. The CPH model will be used for inferences, with treatment group and injection site (abdomen, buttock, or thigh) modelled as categorical effects, and baseline plasma glucose modelled as a continuous covariate. The treatment group rate ratios, active versus placebo, will be estimated together with the 95% confidence intervals, and pairwise

CONFIDENTIAL

Sponsor:	Zealand Pharma A/S	Protocol Number:	ZP4207-16137
----------	--------------------	------------------	--------------

treatment group inferences (dasiglucagon vs placebo, GlucaGen vs placebo) will be evaluated using two-sided likelihood ratio tests.

The key secondary endpoints of plasma glucose changes from baseline changes from baseline within 30 minutes, within 20 minutes, within 15 minutes, and within 10 minutes after study drug injection or at the time of rescue, will be analyzed with the plasma glucose changes from baseline at rescue carried forward in those subjects who require rescue IV glucose before plasma glucose ≥ 20 mg/dL recovery. Each of these changes from baseline variables will be analyzed using an Analysis of Covariance model, with treatment group modelled as a fixed effect and with the baseline plasma glucose modelled as a covariate. The dasiglucagon versus placebo treatment group difference will be evaluated inferentially as a least squares means contrast, using a two-sided t-test at the 0.05 significance level, first for the 30 minute changes from baseline, and then sequentially for the 20 minute, 15 minute, and 10 minute variables, until the first failure to reject.

4.10.1 Center/Study Site Effects

This study will be conducted in 4 countries at 5 study sites. Subjects from all study sites will be pooled. No adjustment for study site will be carried out.

Region	Country	Number of Study Sites	Total Subjects
Europe	Austria	1	80
N. America	Canada	1	40
Europe	Germany	2	35
N. America	USA	1	30

4.11 Protocol Violations or Deviations

Before data are released for statistical analysis, a treatment-masked review of all data will take place to identify protocol deviations that may potentially affect the results. This review will be performed without revealing to which trial product the subjects were assigned. The masking of the trial products will be maintained for everyone involved in allocating subjects to the analysis sets until data are released for statistical analysis. Furthermore, spurious outliers will be evaluated. In addition, protocol deviations that may potentially affect the results will be identified and it will be evaluated if subjects and/or data should be excluded from the analysis. Protocol deviations will be classified as minor or major in a consistent way. Major deviations from the protocol may lead to the exclusion of a subject from the PP set.

Major protocol deviations may include deviations related to trial inclusion or exclusion criteria, conduct of the trial, subject management or subject assessment. Unless explicitly decided

CONFIDENTIAL

Sponsor:	Zealand Pharma A/S	Protocol Number:	ZP4207-16137
----------	--------------------	------------------	--------------

otherwise during the masked data review, the following will be considered major protocol deviations:

- Violation of one or more major inclusion/exclusion criteria
- Interruption of administration of trial product
- Significant deviation from time windows
- Incorrect treatment allocation
- Missing primary endpoint.

The violation of several major inclusion/exclusion criteria or the complete absence of efficacy data might lead to exclusion of the subject from Full analysis set. In that case, the decision should be taken at the blinded data review meeting, and the exclusion from efficacy analysis justified in the signed notes of the meeting.

Obviously erroneous data points may be excluded from the analyses or reanalyzed (in case of e.g., serum concentrations). The decision to reanalyze or exclude data points from the statistical analysis is the joint responsibility of the sponsor and the trial statistician.

The subjects or observations to be excluded and the reason for their exclusion will be documented and signed by those responsible prior to database release. The documentation will be stored together with the remaining trial documentation. The subjects and observations excluded from analysis sets, and the corresponding reasons, will be described in the clinical trial report.

4.12 Subject Withdrawals and Missing Data

Failure is defined for the primary time-to-recovery endpoint as censored with time to recovery set to the maximum follow-up time, here 45 minutes. Individuals will be set to 'failure' in case of receiving rescue IV glucose, discontinuation due to treatment or discontinuation in connection with the induced hypoglycemia state. Only if an intermediate assessment is missing independent of rescue treatment, study treatment or an adverse event including hypoglycemia, a linear interpolation can be applied to impute a missing value.

The same construct of imputation for missing values applies for the analysis of the plasma glucose AUC0-30min.

In the case of subject withdrawal, no imputation of values for PK or PD measurements will be done. Analyses will be done on valid cases only, i.e., no imputation techniques such as last observation carried forward will be applied.

CONFIDENTIAL

Sponsor:	Zealand Pharma A/S	Protocol Number:	ZP4207-16137
----------	--------------------	------------------	--------------

Methods for Handling Missing Dates

All analyses and descriptive summaries will be based on the observed data. For the subject data listings, no imputation of incomplete dates will be applied. The listings will present the incomplete dates without any change.

Missing or Partial Death Dates

- If the entire date is missing, the death date will be imputed as the day after the date of last contact.
- If the day or both day and month is missing, the death date will be imputed to the maximum of the full (non-imputed) day after the date of last contact and the following:
 - If day is missing, day will be 1st of the month
 - If both day and month are missing, death month and day will be January 1st.

Missing Dates in Adverse Events/Concomitant Therapies

Dates missing the day or both the day and month of the year will adhere to the following conventions:

- The missing day of onset of an AE or start date of a therapy will be set to:
 - first day of the month that the event occurred, if the onset yyyy-mm is after the yyyy-mm of first study treatment
 - the day of the first study treatment, if the onset yyyy-mm is the same as yyyy-mm of the first study treatment
 - the date of informed consent, if the onset yyyy-mm is before the yyyy-mm of the first treatment
- The missing day of resolution of an AE or end date of a therapy will be set to:
 - the last day of the month of the occurrence. If the subject died in the same month, then set the imputed date as the death date
- If the onset date of an AE or start date of a therapy is missing both the day and month, the onset date will be set to:
 - January 1 of the year of onset, if the onset year is after the year of the first study treatment
 - the date of the first treatment, if the onset year is the same as the year of the first study treatment
 - the date of informed consent, if the onset year is before the year of the first treatment
- If the resolution date of an AE or end date of a therapy is missing both the day and month, the date will be set to:

CONFIDENTIAL

Sponsor:	Zealand Pharma A/S	Protocol Number:	ZP4207-16137
----------	--------------------	------------------	--------------

- December 31 of the year of occurrence. If the subject died in the same year, then set the imputed date as the death date
- If date is completely missing, then no imputation will be done and the event will be considered as treatment emergent (for AEs) or concomitant (for medications) unless the end date rules out the possibility.

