4.6 Prior and Concomitant Medication

Prior glucagon exposure will be recorded in the eCRF at screening. All concomitant medications will be recorded and/or updated in the eCRF at each visit, i.e., at screening (Visit 1), the dosing visit (Visit 2, prior to the start of the insulin-induced hypoglycemic procedure) and at the follow-up visit (Visit 3).

Subjects using any new concomitant medication resulting in fulfillment of a dosing day exclusion criterion (see Protocol Section 5.5 “Dosing Day Exclusion Criteria”) will be excluded from the dosing visit, but can be rescheduled to one of the following days (1–7 days later). The dosing visit can only be rescheduled once.

Prior and concomitant medications will be coded using the World Health Organization (WHO) Drug Dictionary, version 2017Dec.

Incidence of prior and concomitant medication will be presented by treatment, drug class, and preferred drug name using patients in the Safety analysis set.

Prior medications are those that started and stopped before exposure to study medication; concomitant medications are all medications taken during the study period, including those started before but ongoing at first dose of study drug.

Where a medication start date is partially or fully missing, and it is unclear as to whether the medication is prior or concomitant, it will be assumed that it is concomitant.

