4.9.1.1 Subsets

An overall summary table will be provided showing the number and percentage of subjects with any:

- TEAE
- Severe TEAE
- Serious TEAE
- Drug-related TEAE
- Drug-related severe TEAE
- Drug-related serious TEAE
- TEAE leading to withdrawal
- TEAE with outcome death
- AESI

All other information collected (e.g., action taken) will be listed as appropriate.

Only treatment-emergent adverse events (commencing during or after exposure to study treatment) will be included in the adverse and serious adverse event summaries. Non-treatment-emergent events (starting prior to exposure to study treatment) will be included in the subject listings and flagged but not included in the above summaries. Where an AE start date is partially or fully missing, and it is unclear as to whether the AE is treatment emergent, it will be assumed that it is.

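### Section 4.12 moves a partial start date to the dosing date without checking the stop date, which conflicts with the classification rules in 4.6 and 4.9.1.1

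*SAP*

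**What the plan says.** SAP section 4.12 (Methods for Handling Missing Dates) has three start-date rules that matter here, each covering both adverse events and therapies:

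- Day missing, same month as dosing: the start becomes "the day of the first study treatment, if the onset yyyy-mm is the same as yyyy-mm of the first study treatment".
- Day and month missing, same year as dosing: the start becomes "the date of the first treatment, if the onset year is the same as the year of the first study treatment".
- Date completely missing: "If date is completely missing, then no imputation will be done and the event will be considered as treatment emergent", or concomitant for a medication, "unless the end date rules out the possibility".

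Only the third rule refers to the end date.

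Classification is also addressed elsewhere. Section 4.9.1.1 sets its default for the case "Where an AE start date is partially or fully missing, and it is unclear as to whether the AE is treatment emergent", and only then assumes that the event is treatment-emergent. Section 4.6 has the parallel rule for medications and defines the other category: "Prior medications are those that started and stopped before exposure to study medication". Both sections cover partial as well as fully missing start dates.

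Section 4.12 also says that listings will show incomplete dates unchanged. Section 3.4 counts medication taken during the screening period as concomitant.

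**The concern.** A stop date before dosing settles the matter: the event began before exposure, or the medication started and ended before exposure. The two partial-date rules do not use that information and can place the start after the stop. The rule for records with no start date at all does use it. Neighbouring rules in 4.12 also have limits of this kind: an imputed death date is bounded by last contact, and an imputed stop date by death.

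The SAP does not say whether the flag follows the imputed date in 4.12 or the test of unclear status in 4.6 and 4.9.1.1. No listing shows the imputed start and no adverse event or medication duration table is planned, so setting that flag is nearly the only use the imputed start has. At stake is whether some events and medications that ended before dosing enter the TEAE and concomitant medication summaries.

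**Working it through.** The SAP states no figure to reproduce. The check applies the 4.12 rules literally to example records and compares the result with 4.6 and 4.9.1.1.

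Inputs:

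- Start-date rules from 4.12, as above.
- Duration formula from 4.4: end minus onset plus 1. It is used here only to show the order of the dates.
- Screening visit 3 to 30 days before dosing (3.3.1).
- Arm sizes: 78 dasiglucagon and 39 placebo (3.9); GlucaGen 156 − 78 − 39 = 39, using the total in 3.1.
- Assumed dates: dosing 15 March 2018; consent and Visit 1 on 1 March 2018.

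| Record | Start known as | Stop | Start under 4.12 | End − start + 1 | Class from the 4.12 result | Class under 4.6 / 4.9.1.1 |
|---|---|---|---|---|---|---|
| A, event | March 2018 | 10 March | 15 March | −5 + 1 = −4 | TEAE | not TEAE |
| B, medication | 2018 | 20 February | 15 March | −23 + 1 = −22 | concomitant | prior |
| C, event | March 2018 | 20 March | 15 March | 5 + 1 = 6 | TEAE | TEAE (unclear, so default) |
| D, event | nothing | 10 March | none | – | not TEAE (end-date exception) | not TEAE |
| E, medication | February 2018 | 20 February | 1 March (consent) | −9 + 1 = −8 | prior | prior |

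- A and B are the defect: an impossible order of dates, and opposite classes depending on which section the programmer follows.
- A and D differ only in that A has a known month. The record with more information is the one that can be misclassified.
- C shows that the rule works as intended when the stop is not before dosing.
- E shows that the consent-date rule can also put a start after a stop, but the class does not change.

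B is prior because its stop precedes Visit 1. A case that does not depend on the visit date is a medication started in 2018 (month unknown), stopped in March 2018, with dosing in June 2018. The stop is at least 30 + 31 + 1 = 62 days before dosing (31 March to 1 June), outside any 30-day screening window. The year rule still gives it a June start.

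Applying the end-date exception to partial dates makes A non-treatment-emergent and B prior. C stays a TEAE with start 15 March. Only records with a stop before dosing change class.

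Size per subject: 1/39 = 2.6 percentage points in the placebo or GlucaGen arm, and 1/78 = 1.3 points in the dasiglucagon arm.

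**The case against.** The strongest answer is that the SAP already has the right classification rule. Sections 4.6 and 4.9.1.1 expressly cover partial start dates and restrict the default to unclear cases, and a known stop before dosing is not unclear. A programmer who follows them classifies A and B correctly whatever 4.12 imputes. This stands to the extent that 4.12 does not by itself produce false TEAEs; that requires flagging from the imputed date. It does not remove the conflict, because the SAP gives no order of precedence between the sections.

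Several stronger readings are tempting, but the document does not support them:

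- **Inflated AESI counts.** Both AESI definitions in 4.9.1 require a post-dose finding, so an event that ended before dosing does not qualify whatever its imputed start.
- **Negative durations in the report.** The duration formula is a note in 4.4. The only duration table listed in 5.3 is diabetes duration, and listings keep incomplete dates as recorded.
- **Medications stopped during screening.** Section 3.4 counts these as concomitant without any imputation. The medication part of the point is clear only for those stopped before screening.
- **A rate of misclassification from calendar overlap.** If all 2018 dosing dates and screening lags of 3 to 30 days are weighted equally (an assumption), about 65% of the pre-dose days in the screening window fall in the dosing month. That shows the situation can arise. It does not count records with both a partial start and a known pre-dose stop.
- **A biased treatment comparison.** Affected events ended before dosing, so treatment cannot have caused them, and no mechanism favouring one arm is apparent.

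**Conclusion.** The partial-date rules in 4.12 are wrong as written. They omit a stop-date check that the adjacent rule has, they can give a start later than a known stop, and they conflict with 4.6 and 4.9.1.1 on the class of the same record. Actual misclassification depends on one assumption, that the flag is derived from the imputed date, which the SAP neither states nor excludes.

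The effect is limited to the TEAE and prior/concomitant medication summaries and is probably small. The number of affected records cannot be derived from the document. The per-subject figures of 2.6 and 1.3 points assume the planned arm sizes and a subject not already counted in that category. The primary and secondary efficacy analyses are untouched.

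**What to change.** In 4.12, extend the end-date exception to both partial-date start rules:

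- If the stop date is before dosing, class the record as non-treatment-emergent, or as prior for a medication. For medications stopped during screening, make this consistent with 3.4.
- Never impute a start later than a known stop.
- State that 4.6 and 4.9.1.1 govern classification.
- In all other cases keep the dosing-date imputation, which preserves its conservative intent for unclear records.

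The cost is a sentence or two in the SAP and about one line of derivation code. No new data are needed, and it can be settled before unblinding.
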